13.1.5 Clinical Pharmacology Analyses

13.1.5.1 Pharmacokinetics

For noncompartmental analysis, plasma concentrations will be listed and summarized at each time point using descriptive statistics. Descriptive statistics reported will include the arithmetic mean, SD, CV%, geometric mean, minimum, maximum, and median. Only the range and the median will be reported for T_{max} , as this is a categorical parameter. The PK parameters will also be summarized by treatment using descriptive statistics.

Individual plasma concentration plots and mean data graphs will be produced using both linear and semi-logarithmic scales. Mean data graphs will show plasma concentration profiles by treatment group.

Pharmacokinetic plasma parameter estimates and summaries will be completed for the subjects in the PK population. Testing of PK parameters will be outlined in the SAP.

13.1.6 Safety and Tolerability Analyses

Safety analyses through Day 90 of the Double-blind Period will be conducted using data from the Safety Population and safety analyses in the OLE will be conducted using the OLE Safety Population (as defined in Section 13.1.1). Safety variables include treatment-emergent AEs, clinical laboratory values, vital signs, ECG readings, and physical examination results. No formal inferential analyses will be conducted for safety variables in either period.

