5.3. Summary of Potential Risks and Benefits

Although the primary objective of this study is safety in the patient population with LI, the potential benefits of study participation are that subjects with LI may experience a reduction in their LI symptoms as a result of treatment with trifarotene (CD5789) cream HE1. No other benefits of participation are anticipated.

The potential risks of study participation include those associated with exposure to trifarotene (CD5789) cream HE1 and the risks of medical evaluation, including venipuncture.

Animal studies with CD5789 have shown reproductive toxicity in the embryo-fetal studies. Despite low systemic levels with the CD5789 concentration of 50 µg/g used in patients with acne, CD5789 must not be administered during pregnancy.

When CD5789 is used in the other formulations and/or for other indications and/or with higher concentrations or higher application surface areas, the potential risk of teratogenicity needs to be considered as the safety margin may be lower. Depending on the study population and conditions mentioned above, or other specific requirements, the appropriate contraception method is described in this protocol.

It is unknown whether CD5789 or its metabolites are excreted in human milk. A risk to the newborns/infants cannot be excluded. Lactating women are not eligible for the clinical study.

Certain cutaneous signs and symptoms of irritation and localized reactions at the application site such as erythema, scaling, dryness, stinging/burning, and pruritus may be experienced with use of CD5789. Depending upon the severity of these side effects, subjects may be instructed to reduce the frequency of application or to discontinue use.

Trifarotene cream contains propylene glycol that is mildly irritant to the skin, eyes, and mucous membranes. Trifarotene (CD5789) cream HE1 also contains butylated hydroxytoluene that may cause local skin reactions (e.g., contact dermatitis), or irritation to the eyes and mucous membranes and sodium benzoate that is mildly irritant to the skin, eyes, and mucous membranes.

CD 5789 is mildly irritant to the skin, eyes, and mucous membranes. Therefore, it should not come into contact with the eyes, mouth, or mucous membranes.

There is a potential risk of skin sensitization. If a reaction suggesting sensitivity to trifarotene (CD5789) cream HE1 occurs, the use of the trifarotene cream HE1 must be discontinued.

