6. OBJECTIVES

6.1. Primary Objective

The primary objective is to compare the safety and efficacy of 2 concentrations of trifarotene cream HE1 versus vehicle in subjects with moderate to severe autosomal recessive ichthyosis with lamellar scale, also known as lamellar ichthyosis (LI) after 90 days of treatment.

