7. STUDY DESIGN

7.1. Overall Study Design and Plan

The first part of this study is a phase 2, randomized, 2-cohort, double-blind, vehicle-controlled, multicenter study of the safety, tolerability, PK, and efficacy study of trifarotene cream HE1 100 µg/g and 200 µg/g in subjects with LI for 90 days. Subjects who complete the randomized, double-blind, vehicle-controlled period of the study will be eligible to continue into an open-label extension (OLE) and be treated with trifarotene cream HE1 200 µg/g for an additional 90 days.

The randomized, double-blind, vehicle-controlled period of the study in subjects with moderate to severe LI (i.e., 3–4 on a 5-point Investigator Global Assessment [IGA] scale where 0 = clear; 1 = almost clear; 2 = mild; 3 = moderate; and 4 = severe), is designed to compare the safety of 2 doses of trifarotene cream HE1 with that of vehicle in the treatment of LI.

Upon signing informed consent and entering the Screening Period, subjects will stop using physical and medical treatments for LI, including balneotherapy, and may begin to washout prohibited topical and systemic treatments with designated washout periods (Table 9-2), as applicable. Washout may be up to 90 days, as necessary.

During washout, subjects may continue taking their standard of care of visible skin (face and scalp) for cosmetic reasons and of extremities (palms/soles) to avoid functional consequences on walking or moving their fingers. In the US/EU, this may include compounded emollients with keratolytics (alpha or beta hydroxyl acids) and/or urea. The investigator should approve and document these standard-of-care treatments in the electronic case report form (eCRF). If the standard of care treatments of the face and/or palms/soles contain prohibited medications, they must be stopped at the Baseline Visit. Subjects may shower, but not bathe or swim. The IGA will be evaluated on the rest of the body at Baseline. After completing any necessary washout of prohibited medications, subjects will return to the site to have their LI assessed and to complete the study eligibility requirements.

Study drug will be packaged in 50-g tubes from which up to 36 g of IP may be dispensed per application, i.e., the maximum dose per application.

Study staff will choose 1 tube from the kit dispensed to the subject at that visit, and apply the first dose of study drug to each subject in the clinic on Day 1 after Baseline measurements; they will

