11.3. Special Considerations

11.3.1 Adverse Events of Special Interest

Since topical retinoids are associated with local application site AEs, particularly when beginning treatment, these events will be followed closely during the study and considered AEs of special interest (AESIs).

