13.1.6.1 Local Tolerability

During all clinic visits, the investigator will assess local tolerability (stinging/burning, pruritus, or erythema on 0-3 scales [none, mild, moderate, severe]) for each treated body area (chest/abdomen, back, arms, legs, and face/neck). Descriptive summaries will be presented by period, treatment group, and visit.

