13.1.6.2 Adverse Events

All AEs will be coded using the Medical Dictionary for Regulatory Activities (MedDRA), Version 20.1 or higher.

Treatment-emergent AEs are defined as:

- AEs with onset at the time of or following the start of treatment with IP through the Follow-up Visit or Early Termination Visit, whichever occurs first, or
- AEs starting prior to the start of treatment but increasing in severity or relationship at the time of, or following, the start of treatment with IP through the Follow-up Visit or Early Termination Visit, whichever occurs first.

The number and percentage of subjects with AEs will be displayed by each treatment group in the Double-blind Period and overall in the OLE by system organ class and preferred term. Summaries of AEs by severity and relationship to IP will also be provided. Serious adverse events and AEs resulting in discontinuation of IP will be summarized separately in a similar manner. Subject listings of AEs, SAEs, and AEs causing discontinuation of IP will be produced.

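### The primary objective compares safety with vehicle, but the plan for adverse events and local tolerability is descriptive by arm, with no between-arm estimate, no precision and no total for application-site events

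*Protocol*

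**What the plan says.** Three places in the Protocol put safety against vehicle, or safety itself, at the front of the trial.

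- Section 6.1: "The primary objective is to compare the safety and efficacy of 2 concentrations of trifarotene cream HE1 versus vehicle".
- Section 7.1, on the double-blind period: it "is designed to compare the safety of 2 doses of trifarotene cream HE1 with that of vehicle in the treatment of LI".
- Section 5.3: "Although the primary objective of this study is safety in the patient population with LI".

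The analysis section is descriptive.

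- Section 13.1.6: "Safety variables include treatment-emergent AEs, clinical laboratory values, vital signs, ECG readings, and physical examination results". For these, "No formal inferential analyses will be conducted for safety variables in either period".
- Section 13.1.6.1, on local tolerability, which that list does not mention: "Descriptive summaries will be presented by period, treatment group, and visit".
- Section 13.1.6.2 shows the number and percentage of subjects with AEs in each arm by system organ class and preferred term, with further summaries by severity and by relationship. It adds: "Serious adverse events and AEs resulting in discontinuation of IP will be summarized separately in a similar manner".

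Section 11.3.1 makes local application-site events the AEs of special interest. Section 13.1.6.2 has no row for them as a class. Section 9.4 requires area-level dosing changes for tolerability to be documented in the diary and the eCRF, but Section 13.1.6 plans no summary of them.

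**The concern.** The two halves of one primary objective are treated differently. For efficacy, Section 13.1.4.2 plans odds ratios and differences in proportions against vehicle, with 95% CIs, and P-values. Even the additional responder analyses for roughness and palms/soles in Section 13.1.4.5 get a difference with a 95% CI. AEs and local tolerability get none.

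The risk is in how the results will be read. With small arms, two percentages side by side can be called similar or worse with nothing on the page to show how wide a range of true differences fits the data. Local reactions are where this matters most. Section 5.2 reports that irritation in healthy volunteers forced less frequent application, and Section 7.1 says that local tolerability of this formulation in LI is unknown.

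**Working it through.** **Is there a stated safety figure to reproduce?** No. Section 13.2 sizes the trial on efficacy only. The one remark on safety sizing is in the synopsis, which calls 15 subjects in the first cohort reasonable and gives no rate or precision.

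**Inputs.**
- Arm size: 120 subjects randomized 1:1:1 (Section 13.2), so 120 / 3 = 40 per arm. The Safety population (Section 13.1.1) is everyone randomized with at least one application, so close to 40 per arm. The 32 evaluable per arm in Section 13.2 is an efficacy number.
- Event counts: assumed for illustration, because the protocol gives no expected safety rate.

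**Interval for a difference.** First the Wilson limits for each arm, with z = 1.96:

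(l, u) = [x + z²/2 ± z√n · √(p(1−p) + z²/(4n))] / (n + z²)

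| Events of 40 | p | l | u |
|---|---|---|---|
| 4 | 0.100 | 0.040 | 0.231 |
| 8 | 0.200 | 0.105 | 0.348 |
| 20 | 0.500 | 0.352 | 0.648 |

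Then Newcombe's score interval for d = p1 − p2:

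lower = d − √[(p1 − l1)² + (u2 − p2)²]; upper = d + √[(u1 − p1)² + (p2 − l2)²]

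- 4 v 4: d = 0. The half-width is √[(0.100 − 0.040)² + (0.231 − 0.100)²] = 0.144, so −14.4 to +14.4 points.
- 8 v 4: d = 0.10. Lower = 0.10 − √[(0.200 − 0.105)² + (0.231 − 0.100)²] = −0.061. Upper = 0.10 + √[(0.348 − 0.200)² + (0.100 − 0.040)²] = 0.259. That is +10 points, −6.1 to 25.9.
- 20 v 20: d = 0, −20.9 to +20.9 points.

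**Upper limit with no events.** The two-sided 95% exact limit for 0 of 40 is 1 − 0.025^(1/40) = 0.088, or 8.8%.

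**Can the reader rebuild the missing output?** For any TEAE, or for TEAEs leading to discontinuation of IP, an interval can be worked out by hand if the per-subject count is shown. For application-site events it cannot. A subject with two preferred terms counts in both rows, so the class total lies somewhere between the largest single row and the sum of the rows. A system organ class row does not settle it unless that class happens to hold all the application-site terms and nothing else. The total has to be planned from subject-level data.

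**The case against.** The strongest reply is that a randomized, vehicle-controlled trial which tabulates safety for every arm does compare safety, descriptively, and that this is an ordinary choice in a phase 2 trial sized for efficacy. That stands. It rules out three stronger readings that a reader might infer.

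- *That the safety objective ends without a comparison.* Sections 13.1.6.1 to 13.1.6.6 show the double-blind arms together, and Section 13.1.6.5 announces a comparison of QT results, although it gives no method. The gap is therefore confined here to AEs and local tolerability.
- *That safety gets only counts.* Laboratory values and vital signs get summary statistics, changes from baseline and shift tables; ECG measures get summary statistics. AEs are also summarized by severity and relationship. Local reactions have their own 0-3 scores, assessed by body area and summarized by arm and visit, and these do not depend on how AEs are coded.
- *That the choice between 100 and 200 µg/g will turn on local harm.* No section says so. Sections 5.2 and 7.3 say the doses are studied to find the more effective one, and Section 5.3 already picks 200 µg/g for the extension.

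A second reply is that Section 13.1 is a summary, that the SAP may add descriptive intervals, and that excluding formal inference does not forbid them. That is partly right. The mere absence of an AESI grouping from a protocol would not be a finding. But the protocol itself states a comparative primary objective and itself fixes a rule against inference for safety. A reader cannot tell from it whether between-arm intervals are meant to be shown, and the wording of Sections 6.1 and 7.1 can be settled only in the protocol.

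A third reply is that several unadjusted intervals invite being read as tests. That is a real but small cost, and labelling deals with most of it.

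**Conclusion.** The point holds in limited form. The protocol sets out to compare safety with vehicle, and for AEs and local tolerability it plans by-arm description with no effect estimate and no precision. It plans no once-per-subject figure for the events it singles out as being of special interest.

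At about 40 per arm the unseen uncertainty is large: equal counts of 4 are compatible with a true excess of up to 14 points, and no events with a true rate of up to 8.8%. These sizes rest on assumed event counts and on nearly all randomized subjects receiving at least one application. They show ordinary imprecision at this sample size; they do not show that any number in the protocol is wrong. No hypothesis test on safety is needed, and the descriptive plan is not invalid. This is a cheap improvement that should be made, and it does not threaten the trial.

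**What to change.** In Section 13.1.6, keep the position that no hypothesis tests will be done on safety. Add, for the Double-blind Period and the Safety population, the difference in proportions of each dose minus vehicle with a 95% score interval for four outcomes:

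1. any TEAE;
2. any application-site TEAE (the Section 11.3.1 class), counted once per subject;
3. any TEAE leading to discontinuation of IP;
4. any body area with application reduced or interrupted under Section 9.4.

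Label the table descriptive and unadjusted for multiplicity. The term list that defines outcome 2 can sit in the SAP.

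The cost is one table. AEs and dosing changes are already recorded in the eCRF, so no new data are needed. The downside is 4 outcomes × 2 doses = 8 unadjusted intervals that must not be read as tests.

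If the sponsor prefers not to add the table, reword Sections 6.1 and 7.1 so that they say the safety comparison is descriptive. That costs a sentence and removes the mismatch, but it leaves the precision unreported.

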13.1.6.1 Local Tolerability

During all clinic visits, the investigator will assess local tolerability (stinging/burning, pruritus, or erythema on 0-3 scales [none, mild, moderate, severe]) for each treated body area (chest/abdomen, back, arms, legs, and face/neck). Descriptive summaries will be presented by period, treatment group, and visit.

13.1.6.2 Adverse Events

All AEs will be coded using the Medical Dictionary for Regulatory Activities (MedDRA), Version 20.1 or higher.

Treatment-emergent AEs are defined as:

- AEs with onset at the time of or following the start of treatment with IP through the Follow-up Visit or Early Termination Visit, whichever occurs first, or
- AEs starting prior to the start of treatment but increasing in severity or relationship at the time of, or following, the start of treatment with IP through the Follow-up Visit or Early Termination Visit, whichever occurs first.

The number and percentage of subjects with AEs will be displayed by each treatment group in the Double-blind Period and overall in the OLE by system organ class and preferred term. Summaries of AEs by severity and relationship to IP will also be provided. Serious adverse events and AEs resulting in discontinuation of IP will be summarized separately in a similar manner. Subject listings of AEs, SAEs, and AEs causing discontinuation of IP will be produced.

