10.2.3 Follow-up Telephone Call (± 14 days after Day 90) – Only Subjects Who Do Not Continue into Open-label Extension

Clinic staff will telephone subjects who choose not to continue into the Open-label Extension within 14 days after Day 90 to assess any ongoing AEs.

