11.1.6 Treatment-Emergent Adverse Events

An AE is defined as treatment emergent if the first onset or worsening is after the first application of IP (trifarotene or vehicle) and not more than 14 days after the last application of IP.

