11.2.1 Assessment

The investigator is responsible for the detection and documentation of events meeting the criteria and definition of an AE or SAE described previously. At each visit, the subject will be allowed time to spontaneously report any issues since the last visit or evaluation. The investigator will then monitor and/or ask about or evaluate AEs using nonleading questions, such as

- “How are you feeling?”
- “Have you experienced any issues since your last visit?”
- “Have you taken any new medications since your last visit?”

Any clinically relevant observations made during the visit will also be considered AEs. In addition, although local tolerability will be assessed on a 0-3 scale, all application site reactions should be recorded as AEs.

The Tolerability Assessments Form at each visit collects a numeric severity score by body area for erythema, stinging/burning, and pruritus.

In addition, if skin irritation is more than the expected erythema, stinging/burning, and pruritus with the application of this topical retinoid (i.e., clinically relevant), please enter the application site reactions in the Adverse Event description section. If a diagnosis is known, record the diagnosis. If a diagnosis is known and there are other signs/symptoms that are not generally part of the main diagnosis, record the diagnosis and each sign/symptom on a separate line. If a diagnosis is not known, record each sign/symptom on a separate line. Examples are allergic contact dermatitis, sunburn, skin erosion, and swelling.

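### The protocol gives two treatment-emergent windows and two recording rules for application-site reactions, so TEAE and special-interest counts depend on which section is followed

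*Protocol*

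**What the plan says.** **Treatment emergence.** Protocol Section 11.1.6 reads: "An AE is defined as treatment emergent if the first onset or worsening is after the first application of IP", with the limit "not more than 14 days after the last application of IP". Section 13.1.6.2, which introduces the adverse-event tables, ends the window differently: "through the Follow-up Visit or Early Termination Visit, whichever occurs first". It also counts "AEs starting prior to the start of treatment but increasing in severity or relationship", so a pre-existing event whose judged relationship alone goes up is treatment-emergent there. It is not under 11.1.6.

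**Follow-up.** Section 10.1.1 places follow-up 14 days after the last application. For subjects who do not enter the open-label extension (OLE), Section 10.2.3 provides a telephone call "within 14 days after Day 90 to assess any ongoing AEs"; its heading gives the timing as ±14 days. Section 11.2 requires nonserious events to be recorded until 14 days, and serious ones until 30 days, after the last day of participation.

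**Application-site reactions.** Section 11.2.1 states that "all application site reactions should be recorded as AEs", and Section 10.3.4.2.4 likewise has all of them recorded in the diary as TEAEs. A later paragraph of 11.2.1 tells sites to enter them in the adverse-event section "if skin irritation is more than the expected erythema, stinging/burning, and pruritus with the application of this topical retinoid (i.e., clinically relevant"). Section 11.3.1 makes local application-site events the adverse events of special interest (AESIs).

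**The concern.** Safety is part of the primary objective, and local reactions are the events that Section 11.3.1 singles out for close follow-up. Adverse events are tabulated by treatment group, so they need one counting rule and one recording rule.

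On the window, one section ties the end to exposure and the other to a visit. Whether an event after stopping counts then depends on the section the programmer follows and on how the subject left the study.

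On local reactions, the conflict acts earlier, at data entry. A site following the first sentence of 11.2.1 enters every reaction; a site following the later paragraph enters only those beyond an undefined expected level. A reaction never entered as an adverse event cannot be restored in the analysis.

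**Working it through.** The protocol states no TEAE or AESI rate, so there is no figure to reproduce. The check compares the day on which each window closes.

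**Inputs**
- Window A (11.1.6): last application + 14 days.
- Window B (13.1.6.2): Follow-up Visit or Early Termination (ET) Visit, whichever is first.
- Earliest ET visit: Visits 6 and 10, which double as the ET visits (10.2.2.7 and 10.2.4.6), include a PK sample, and Section 9.2 requires PK visits at least 24 hours after the last application. So B closes no earlier than last application + 1 day, and the largest shortfall is 14 − 1 = 13 days.
- Subjects who stop study drug but keep attending have Day 90 as scheduled (Table 2-1, footnote b).

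**Closing day and difference (B − A), nominal days**

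| Case | Last application | A closes | B closes | B − A |
|---|---|---|---|---|
| ET visit 1 day after stopping | 30 | 44 | 31 | −13 |
| ET visit 7 days after stopping | 30 | 44 | 37 | −7 |
| Stops Day 14, attends to Day 90 | 14 | 28 | 90 | +62 |
| Stops Day 30, attends to Day 90 | 30 | 44 | 90 | +46 |
| Double-blind completer, no OLE, call Day 91 | 87 (assumed) | 101 | 91 | −10 |
| Double-blind completer, no OLE, call Day 104 | 87 (assumed) | 101 | 104 | +3 |
| OLE completer, follow-up at 14 days | 180 | 194 | 194 | 0 |

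The +62 and +46 rows take Visit 6 as the closing visit. If the later follow-up call closes the window instead, B runs up to 14 days longer. The call rows treat the call as the Follow-up Visit, since no other follow-up is scheduled for these subjects.

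**How many subjects.** Section 13.2 allows 20% for drop-out/nonevaluable: 0.20 × 120 = 24, which matches 120 − 3 × 32 = 24. This caps the planned number of early terminators; it does not estimate it.

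**Collection.** Section 11.2 needs nonserious events up to 14 days after participation ends. A call on Day 91 about ongoing events satisfies 10.2.3, and no later contact is scheduled for these subjects.

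**Application-site reactions (illustration; both rates are assumed).** Let 30% to 70% of the 40 subjects per arm (120/3) have any reaction, and 10% to 50% of those exceed the expected level.
- All reactions recorded: 40 × 0.30 = 12 to 40 × 0.70 = 28 subjects per arm.
- Only those beyond expected: 12 × 0.10 = 1.2 to 28 × 0.50 = 14 subjects per arm.

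**The case against.** A reader might infer that 24 subjects each lose 14 days of observation and that TEAEs are therefore understated most in the arm with more tolerability drop-outs. The documents do not support that:

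- The 20% includes nonevaluable subjects as well as drop-outs, and the 24-hour PK rule caps the loss at about 13 days.
- For subjects who stop study drug but keep attending, the 13.1.6.2 window is longer, so the direction is mixed.
- Section 11.2 already requires events after participation to be recorded. An event outside the window loses its treatment-emergent label, but Section 13.1.6.2 still lists all adverse events.
- Tables count subjects. Someone who stops because of a reaction normally has a qualifying event already, and events leading to discontinuation are summarised separately.

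On local reactions, the 0-3 scores by body area are collected at clinic visits and summarised by arm and visit (13.1.6.1) under either rule. Safety has no formal inference (13.1.6), and no between-site AESI comparison is planned. The later paragraph of 11.2.1 can also be read as a deliberate split, with expected irritation on the tolerability form and anything more in the adverse-event section.

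These points limit the size and remove the claimed direction. The contradictions remain. If every reaction is already an adverse event, a more-than-expected condition has no function, so the split reading conflicts with the sentence before it and with 10.3.4.2.4. A SAP could settle the window, but it cannot recover reactions that were not entered or fix the timing of a call.

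**Conclusion.** The point holds as two contradictions in the current text.

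- **Window.** Sections 11.1.6 and 13.1.6.2 define different TEAEs. Relative to 11.1.6, the 13.1.6.2 window runs from about 13 days shorter to, in the examples, 62 days longer, and it coincides for OLE completers followed exactly 14 days after the last application. At most 24 subjects could be early terminators under the planning allowance. The net direction by arm cannot be computed from the documents.
- **Collection.** For double-blind completers not entering the OLE, the scheduled call does not secure the 14 days that 11.2 requires.
- **Local reactions.** AESI incidence depends on which sentence of 11.2.1 a site follows. This probably affects counts more than the window does, because it cannot be repaired afterwards. Its size is unknown, since the illustrated ranges rest on assumed rates. Local tolerability data as such are not lost.

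The day counts assume nominal visit days, and a last application on Day 87 for the non-OLE rows. This should be corrected; it does not invalidate the design.

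**What to change.** 1. Use one TEAE definition in both sections. Align 13.1.6.2 to the exposure-based window of 11.1.6 (last application + 14 days), and settle whether a rise in relationship alone counts.
2. Time the existing call for subjects not entering the OLE so that it closes that window, and have it ask about new as well as ongoing events. Bring the heading and text of 10.2.3 into line.
3. Reconcile 10.3.4.2.4 and 11.2.1 to a single recording rule applied at all sites. The sponsor should choose which: the documents support reconciliation, not one rule over the other. Report the 0-3 tolerability scores alongside AESI incidence.

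The cost is minor rewording of these sections and, depending on the rule chosen, more mild events to record. The call already exists. No contact after an Early Termination Visit is explicitly scheduled. Adding one would be a new procedure with its own cost, and it is not part of this change.
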